An electronic database for data entry and management (using VA REDCap or other comparable software) will be built. We will perform all data analyses using STATA15 other available statistical package. A statistician will be available for consultation in statistical design and analyses but will not have access to identifiable patient data. The full analysis set will be based on an intention-to-treat (ITT) analysis, which will comprise all participants who have been randomized to either study arm, regardless of length of follow-up or actual intervention received. As

a preventive measure, every attempt will be made to document all reasons for missing data and will compare the rates of lost-to-follow-up between study arms. In addition, baseline characteristics will be compared between participants who do and do not withdraw from the study, to assess the impact of missing information and attrition.

Demographic and baseline characteristics (e.g., demographics, combat status, alcohol and substance use disorders, medication use, health services use) will be presented as mean and standard deviations for continuous variables and sample proportions for categorical variables. All descriptive statistics will be accompanied by 95% confidence intervals. Baseline comparisons between study arms (for each hypothesis) will be performed using t-tests for continuous variables, chi-squared tests for categorical variables, or their nonparametric counterparts. Diagnostics (i.e., conditional studentized residuals, plots of outcomes over time) will be performed on each linear mixed model to assess whether necessary assumptions were met.

To assess feasibility, the number of participants approached each month, the proportion who enroll, the rate and timing of dropouts, the proportion of referring providers, and the number of study care manager contacts will be calculated. Additionally, Vets Prevail program usage data, including the proportion of participants in the intervention arm who become registered users, enroll in the cCBT program, and complete the entire cCBT program will be calculated; Vets Prevail data will be further aggregated to understand average/median duration of and number of completed cCBT sessions, community message board posts, and peer chats.

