To quantify acceptability, summary statistics (e.g., median/mean) for CSQ-I items scores will be computed. Under an health anthropologist's guidance, responses to the open-ended survey questions will be categorized as positive, neutral, negative, or ambivalent. Responses will be independently coded by multiple people, resolving disagreements through discussion and examining positive and negative factors.¹⁵

[figure not shown]
To assess feasibility, acceptability, and other depression related outcome measures, generalized linear mixed model (GLMM) will be used, which provides a unified framework for the analysis of outcome trajectories over time by allowing for the modeling of repeated measures for each participant. GLMM is robust to imbalanced designs and provides unbiased estimates even when data are missing at random. GLMM will be fit as a function of study arm, time, time-by-study arm, and gender. In addition, the intercept will be allowed to vary randomly to account for subject-level variability of the outcome at baseline. [standard errors will be adjusted to account for provider/clinic clustering.] Analyses will first be conducted on complete data only and will estimate the adjusted mean difference in 3-month improvement on PHQ-9 (depression symptoms), GAD-7 & PCL-5 (other mental health symptoms), PROMIS (HRQoL), and BADS-SF/PAM-13 (behavioral/patient activation) between cCBT-enhanced collaborative care and control arms. As an exploratory measure, we will conduct additional analyses on study outcomes using predefined numbers of completed cCBT sessions (e.g., >2 sessions, all 5 sessions).

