Sample Sizes and Power Analyses: The primary purpose of this pilot is to assess feasibility of trial methods, including recruitment, intervention, and follow-up. Nevertheless, given the sample sizes we plan to enroll, the trial will have the power to detect an effect size (ES) of 0.78 or greater ITT on the PHQ-9 of cCBT-enhanced collaborative care versus UC patients at 3-month follow-up. Data are based on Richards et al's 2014 study,¹⁰ which reported a d=0.78 ES for therapist-guided cCBT trials for improving depression outcomes, which is slightly higher than the reported ES (d=.56) for the Vets Prevail RCT. This is consistent with literature showing that therapist support yields greater effects for cCBT.¹⁰ Assuming an 80% 3-month assessment completion rate (consistent with prior relevant studies)¹²⁻¹⁴ and 2-tailed type I error of 0.05, if 37 subjects are enrolled to the intervention arm and 37 to the control arm (74 total) 80% power to detect at least a 0.78 ES improvement of cCBT-enhanced collaborative care over usual care on the PHQ-9 (primary hypothesis) will be achieved. The pilot

is not powered to detect changes in HRQoL. We lack pre-existing data to estimate effects on behavioral/patient activation. It is underpowered to detect differences by gender. Other analyses, e.g., access, is exploratory.

8. Timeline

Project Timeline

9. Relevant publications

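### The plan confines the between-arm mixed model to complete data; read as both-visit participants, this drops about 15 of 74 randomised and conflicts with the plan's own ITT set

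*Combined protocol and SAP*

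**What the plan says.** Section 7 (Data Analysis) declares an intention-to-treat full analysis set, "which will comprise all participants who have been randomized to either study arm, regardless of length of follow-up or actual intervention received". It specifies a generalised linear mixed model with arm, time, arm-by-time, gender and a random intercept, and supports that choice by saying that the model "provides unbiased estimates even when data are missing at random". It then says: "Analyses will first be conducted on complete data only and will estimate the adjusted mean difference in 3-month improvement on PHQ-9". The same sentence covers GAD-7, PCL-5, PROMIS, BADS-SF and PAM-13.

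What counts as complete data is not defined. The next sentence moves to another question: "As an exploratory measure, we will conduct additional analyses on study outcomes using predefined numbers of completed cCBT sessions". The remaining provisions for missing data are descriptive. Reasons are documented, loss to follow-up is compared between arms, and "baseline characteristics will be compared between participants who do and do not withdraw from the study".

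The sample-size text in Sections 4.2 and 7 frames the comparison as "an effect size (ES) of 0.78 or greater ITT on the PHQ-9", "Assuming an 80% 3-month assessment completion rate". Section 4.3 gives two assessments, at baseline and 3 months. Section 4.1 puts the baseline interview straight after consent.

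**The concern.** With two visits and baseline taken at consent, a participant with incomplete PHQ-9 data is in practice one who missed month 3. If complete data means both visits, that person belongs to the declared analysis set but not to the analysis. The model is then fitted to balanced data, its arm-by-time term becomes a plain completers' contrast, and the missing-at-random argument for choosing it no longer applies.

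At stake is the PHQ-9 estimate that will inform the larger trial. The two possible fits agree when dropout is unrelated to severity, or related to it in the same way in both arms. They part when the relation differs by arm. That is conceivable here because only the intervention arm has weekly care-manager contact (Section 4.3). With the phrase undefined, the choice between the fits could be made after the data are seen.

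**Working it through.** **Inputs from the documents.** 37 per arm, 74 in total; 80% completion at 3 months; effect size 0.78; two-sided 0.05; 80% power (Sections 4.2 and 7). Two visits (Section 4.3). Entry requires PHQ-9 of 10 or more (Section 5.3).

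**Inputs assumed.** Baseline-to-3-month correlation ρ = 0.3 to 0.7. Dropout is logistic in severity with log-odds 0.7 to 1 per SD, in one arm only, calibrated to 20% missing per arm. The documents give none of these.

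**1. The plan's power figure.** n per arm = 2(1.960 + 0.842)² / 0.78² = 25.8, so 26 (27 with the t distribution). Dividing by 0.80 gives 33 (34), against 37 planned. Completers number 37 × 0.80 = 29.6 per arm. A two-sample t-test has 83.1% power at 29 and 84.4% at 30. The stated 80% therefore holds as a floor, and it already counts completers only, so the present point does not touch it.

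**2. Who is dropped.** On the both-visits reading 74 × 0.20 = 14.8, about 15 participants, leave the analysis. It uses 2 × 59.2 = 118.4 observations, against 74 + 59.2 = 133.2 if every observed value is kept.

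**3. What the model estimates on both-visit data.** In 60 simulated trials of 37 per arm with the plan's model terms, the arm-by-time estimate equalled the difference in completers' mean change (largest discrepancy 1.4e-15).

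**4. Bias, dropout driven by baseline score.** Let δ be the shift in completers' mean baseline in the affected arm, in SDs. Completers' mean change is then off by (ρ − 1)δ. Under the assumed dropout model δ = −0.13 at log-odds 0.7 and −0.17 at log-odds 1.
- Smallest: (0.7 − 1)(−0.13) = 0.04 SD.
- Largest: (0.3 − 1)(−0.173) = 0.12 SD.
- The standard error of the contrast is √(2(1 − ρ)) × √(2/29.6) = 0.31, 0.26 and 0.20 SD for ρ = 0.3, 0.5 and 0.7. In finite-sample simulation the bias is 0.19 to 0.40 of a standard error, and the false-positive rate is 5.5% to 7.0%.
- The all-observed likelihood fit has bias of about 0.
- With the same dependence in both arms, the two δ terms cancel and both fits have bias of about 0.

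Whether the shift flatters or penalises the intervention depends on which arm is affected.

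**5. Bias, dropout driven by unobserved stable severity.** The order reverses. Completers' change has bias of about 0. The all-observed fit is off by (1 − ρ)√ρ × δ, from 0.3 × 0.837 × (−0.13) = −0.03 to 0.7 × 0.548 × (−0.173) = −0.07 SD.

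**6. Effect of the entry cutoff.** Requiring PHQ-9 of 10 or more narrows baseline variance relative to month 3. With baseline truncated at −1 or 0 SD (assumed), log-odds 1 on baseline score and one arm affected, in 3-month SDs:
- completers' contrast: about 0.04 to 0.11;
- all-observed fit with a random intercept only: −0.01 to −0.04;
- all-observed fit with residual variance differing by visit: about 0.

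**7. Precision.** The standard error is 0.20-0.31 SD for completers and 0.20-0.30 SD for the all-observed fit.

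**The case against.** The strongest reply is that the plan is already consistent. If complete data means observed values without imputation, baseline-only participants stay in the mixed model, and the ITT set and the missing-at-random rationale both stand. Those two statements suggest that such a fit is probably intended. This part of the reply stands, and it makes the conflict conditional on the both-visits reading. It does not remove the point, because the word only pulls towards that reading and nothing in the text settles it.

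A reader might infer that no main analysis is named, or that a promised second step has gone missing. The documents do not support either. Model, terms, contrast, outcomes and analysis set are all given. The word first may simply place the between-arm estimate ahead of the exploratory analysis by sessions completed.

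A reader might also infer that the PHQ-9 result will be biased. That is not supported. The bias needs dropout to depend on severity differently by arm, and care-manager contact is thin evidence for it. The 3-month interview is conducted by a research assistant and carries the same voucher in both arms, and stopping the online sessions is not the same as missing month 3. Nor does the all-observed fit win under every mechanism (step 5). Comparing the two fits would not show which to trust: completers minus all-observed is positive under both one-arm mechanisms (0.04-0.12 and 0.03-0.07 SD), with a sampling SD of 0.04-0.09 SD.

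**Conclusion.** The point holds in limited form. On its plain reading, the complete-data restriction excludes about 15 of 74 randomised participants and contradicts three of the plan's own statements: the all-randomised set, the ITT label on PHQ-9 and the reason for using a mixed model. The attrition checks in Section 7 would help reveal differential dropout, but they supply no all-randomised estimate.

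The size rests on the assumptions listed in the working: 0.04-0.12 SD, at most 0.40 of a standard error, if dropout follows baseline severity in one arm only. The documents do not say which dropout pattern to expect. The case for change is therefore consistency with the plan's own commitments, not a demonstrated bias.

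Severity is low. Section 7 says that "The primary purpose of this pilot is to assess feasibility of trial methods", and Section 2 claims only that improvement may be reported. Even so, the sample-size text attaches the primary-hypothesis label to the PHQ-9 comparison, so its analysis population should be unambiguous.

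**What to change.** In Section 7, replace the complete-data phrase with:

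*The main analysis fits the mixed model by (restricted) maximum likelihood to all randomised participants, using every observed baseline and 3-month value, with residual variance allowed to differ by visit; the analysis restricted to participants with both visits is a sensitivity analysis.*

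The visit-specific variance belongs in the main specification, because without it the entry cutoff leaves a small bias in the all-observed fit (step 6).

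The cost is one sentence of wording, with the same data and software. The downside is reliance on missing at random: about 0.03-0.07 SD of bias if dropout depends on unobserved stable severity in one arm only, and up to 0.13 SD if it does so in opposite directions in the two arms, which nothing in the documents suggests. Almost no precision is gained. If the sponsor already intends this analysis, the edit simply records it.

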Our primary hypothesis is that cCBT-enhanced collaborative care will be feasible and acceptable among Veterans in primary care. We also hypothesize that patients receiving cCBT-enhanced collaborative care may report moderate improvements in depression symptoms, compared to patients receiving UC at 3-months follow-up. Finally, we hypothesize that the cCBT-enhanced group will have improvements in behavioral/patient activation, health-related quality of life, and other mental health symptoms, compared to UC patients.

3. Activities Overview

Study participants will be randomized to either Usual Care (UC), typically medication, under their own PCP or the Intervention. Those in the intervention arm will receive cCBT-enhanced collaborative care supported by a depression care manager. The depression care manager (a licensed social worker) will facilitate access to cCBT, promote and monitor cCBT use, reinforce CBT concepts (during outside CBT session “homework”), and monitor mental health symptoms for each participant. Participants will be contacted weekly via 15-30-minute phone calls or by other means (e.g., email, Vets Prevail platform). Additionally, a Primary Care and a Psychiatry Consultant will meet weekly with the depression care manager in order to oversee study patient progress and the cCBT-enhanced collaborative care model broadly.

Computer-based CBT (cCBT) will be provided via the VA-sponsored Vet’s PrevailSM program. This program is free for all Veterans, provides self-paced CBT lessons tailored to patients based on sociodemographics, and engage

users with modest financial incentives (e.g., gift cards). It also features a community message board, a peer support specialist chat support, and safety monitoring that includes warm-handoffs to the VA Crisis Chat Line.

4. Study Design

This is a 2-year pilot randomized control trial to assess the feasibility, acceptability, and potential effects of a cCBT-enhanced collaborative care model on depression symptoms and related outcomes.

Eligible and consenting patient subjects will be randomly assigned to one of two treatment conditions: 1) cCBT-enhanced collaborative care (n=37), or 2) usual care (n=37). Randomization to condition will be stratified by gender, to account for differences in care delivery structure and for in treatment outcomes.

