4.2. Sample description, development and rationale

74 (37 male, 37 female) Veterans will be recruited from the Greater Los Angeles Healthcare System, using a mix of purposive and convenience sampling. Purposive sampling will entail using electronic medical records (e.g.,

services utilization, depression diagnostic codes and/or screening data from CDW or other database) for targeted mailing of recruitment letter and flyer. Convenience sampling will entail posting flyers on physical buildings and social media, accepting referrals from providers.

Sample Sizes and Power Analyses: The trial will have the power to detect an effect size (ES) of 0.78 or greater ITT on the PHQ-9 of cCBT-enhanced collaborative care versus UC patients at 3-month follow-up. Data are based on Richards et al's 2012 study,¹⁰ which reported a d=0.78 ES for therapist-guided cCBT trials for improving depression outcomes. This is consistent with literature showing that therapist support yields greater effects for cCBT.¹⁰ Assuming an 80% 3-month assessment completion rate (consistent with prior relevant studies)¹²⁻¹⁴ and 2-tailed type I error of 0.05, if we then enroll 37 subjects to the intervention arm and 37 to the control arm (74 total) we will have 80% power to detect at least a 0.78 ES improvement of cCBT-enhanced collaborative care over usual care on the PHQ-9 (primary hypothesis). The pilot is not powered to detect changes in HRQoL or differences by gender.

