Participants will be assessed in both conditions at baseline and 3 months (post-intervention) via 45-60 minute telephone interviews. The baseline assessment will measure depression and other mental health symptoms; health-related quality of life; patient activation; demographics; physical and mental health comorbidities; substance use history; and treatment utilization. The 3-month assessment will re-measure depression and other mental health symptomatology; health-related quality of life; patient activation, plus assess intervention group participants' satisfaction with treatment; cCBT program usage; and interactions with care management. Intervention entails the cCBT-enhanced collaborative care, using VA-sponsored Vets Prevail.

Compensation: Participants will be compensated with \$30 VCS vouchers for completing the baseline assessment and a \$45 VCS voucher for completing the 3-month assessment (\$75 total). Vouchers will be distributed at the time assessments are completed.

5. Recruitment and Consent

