5.3. Inclusion/Exclusion Criteria

Inclusion:

- Have access to computer (mobile or desktop), internet, telephone, and email

- Able to read English text on a computer screen
- Score 10 or higher on the PHQ-9

Exclusion:

- Have moderate-high suicide risk (e.g., suicide flag) or active suicidality
- Have other serious mental illness (e.g. bipolar disorder, psychosis) or medical disorder that would prevent/interfere with participation (e.g. dementia/cognitive impairment, terminal illness).

6. Data Sources and variables

Study team members will perform baseline (0-month) and 3-month (post-intervention) assessments.

Deidentified data (containing study participant ID) will be entered into VA REDCap or a comparable database which supports trial data and will then be exported securely for analyses after study conclusion. See Table 3 for a list of primary and secondary outcomes and covariates.

	Constructs	Measures	Data Source
Primary Outcomes	Acceptability	Client Satisfaction Questionnaire (CSQ-8), Open-ended questions (likes, disliked, suggestions for improvement)	Patient
	Feasibility	Number, proportion, and representativeness of participants	Patient
	Recruitment	Reasons for declined participation and/or study termination	Study Data
	Intervention	Number, proportion, and representativeness of referring providers	Study Data
	Depression	Number, duration, and type of care manager contacts cCBT usage activity (registration, enrollment, completion, messaging)	Vets Prevail
Secondary	Quality of life	Promis-10 Global Health	Patient
	Activation	Behavioral Activation for Depression Scale (BADS-SF)	Patient
	Anxiety	Patient Activation Measure (PAM-13)	Patient
	PTSD	Generalized Anxiety Disorder (GAD-7)	Patient
		PTSD Checklist for DSM-5 (PCL-5)	Patient
Covariates	Demographics	Age, gender, race/ethnicity, marital status, education level, employment status, and housing status	Patient
	Other patient information	Distance from home to clinic, combat status, service connection, medical & psychiatric diagnosis, empaneled PCP	Chart
	Alcohol use	Alcohol Use Disorders Identification Test (AUDIT-C)	Review
	Substance use	Single Item Drug Screen	Patient
	Antidepressant use	Single Item Cannabis Use	Patient
	Health services use	Per medication list (6 months before & after intervention)	Chart review
		Mental health, PCOMHI, primary care, etc. (6 months before)	Patient
Legend: Implementation outcomes shaded in gray			
Table 3: Data Sources.			

7. Data Analysis

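### The PHQ-9 model tests change without adjusting for baseline PHQ-9, which gives up precision already collected, and the 80% power statement is not tied to that model

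*Combined protocol and SAP*

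**What the plan says.** Sections 4.2 and 7 both state "80% power to detect at least a 0.78 ES improvement of cCBT-enhanced collaborative care over usual care on the PHQ-9", from 37 patients per arm and a two-sided type I error of 0.05. On attrition: "Assuming an 80% 3-month assessment completion rate". Neither section names the test, the SD in which 0.78 is expressed, or a correlation between baseline and 3-month PHQ-9. Both place the effect at 3-month follow-up.

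Section 7 specifies the analysis: "GLMM will be fit as a function of study arm, time, time-by-study arm, and gender". It adds a random intercept and, in square brackets, standard errors adjusted for provider or clinic clustering. The target is then given: "Analyses will first be conducted on complete data only and will estimate the adjusted mean difference in 3-month improvement on PHQ-9". Baseline PHQ-9 is not listed as a covariate. Table 1 in section 4.1 shows the PHQ-9 collected at two points only, before and after the intervention.

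On the size of effect, section 2 hypothesises that intervention patients "may report moderate improvements in depression symptoms, compared to patients receiving UC at 3-months follow-up". Section 7 takes 0.78 from a meta-analysis of computer-based treatment, "which is slightly higher than the reported ES (d=.56) for the Vets Prevail RCT". It also says that feasibility is the pilot's main purpose.

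**The concern.** The power claim and the analysis are described separately, and nothing links them. A comparison of 3-month scores, a comparison of change and a baseline-adjusted comparison have different variances when based on the same patients. With only two visits, the section 7 model amounts to the second of these, so its power depends on r, which the plan does not give.

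Two things are at stake. First, a change analysis is in general less precise than one that adjusts for baseline, and the baseline PHQ-9 is collected in any case. Second, the power text labels the PHQ-9 comparison the primary hypothesis, and the pilot is meant to prepare a larger trial. A reader of a non-significant PHQ-9 result would assume 80% power for the model actually fitted, and the plan does not show that.

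**Working it through.** **Inputs from the documents.** 37 per arm, 80% completion, two-sided 0.05, effect 0.78 (sections 4.2 and 7); two PHQ-9 assessments (Table 1). Evaluable per arm: n = 37 × 0.80 = 29.6.

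**Assumptions, not in the documents.** r = 0.3, 0.5 or 0.7. The ratio k of baseline SD to 3-month SD is 1 or 0.7. The lower value allows for the entry rule "Score 10 or higher on the PHQ-9", which may narrow the baseline spread. Effects are in 3-month SD units unless stated. No clustering allowance is made until step 6. Power is from the noncentral t distribution.

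**1. The plan's own figure.** For an unadjusted t-test at 3 months the noncentrality is d√(n/2) = 0.78 × √14.8 = 3.00 on 57.2 df. Power is 83.9%, so the stated 80% is met, on the conservative side.

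**2. What the section 7 model tests.** On complete pairs, the time-by-arm term is a within-patient contrast. Gender and the random intercept cancel, leaving the difference between arms in mean change. Random-intercept fits to two simulated data sets gave −0.9943 (SE 0.2748) and −0.8705 (SE 0.2324), identical to the difference in mean change and its SE.

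**3. Variances, in units of the 3-month variance.**
- Change: k² + 1 − 2rk. The SD is 1.183, 1.000, 0.775 for k = 1 and 1.034, 0.889, 0.714 for k = 0.7 (r = 0.3, 0.5, 0.7).
- Baseline PHQ-9 as covariate: 1 − r², whatever k is, with one df fewer. The SD is 0.954, 0.866, 0.714.

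The SE ratio, change to covariate-adjusted, is √[(k² + 1 − 2rk)/(1 − r²)]. For example, at k = 1 and r = 0.3 it is √(1.40/0.91) = 1.24.

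| | r = 0.3 | r = 0.5 | r = 0.7 |
|---|---|---|---|
| SE ratio, k = 1 | 1.24 | 1.15 | 1.08 |
| SE ratio, k = 0.7 | 1.08 | 1.03 | 1.00 |
| Power at 0.78, section 7 model, k = 1 | 70.3% | 83.9% | 96.8% |
| Power at 0.78, section 7 model, k = 0.7 | 81.4% | 91.3% | 98.5% |
| Power at 0.78, baseline-adjusted | 87.1% | 92.6% | 98.5% |

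**4. Where a shortfall would begin.** The section 7 model reaches 80% at 0.78 when r is 0.446 (k = 1) or 0.272 (k = 0.7). If dropouts' baselines are kept in the model (37 per arm at baseline, k = 1), power at r = 0.3 is 73.4% and the threshold falls to r = 0.41.

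**5. The other reading of 0.78.** If 0.78 is in SDs of change, the change analysis has the noncentrality of step 1, and power is 84% at any r.

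**6. Clustering.** With an assumed design effect of 1.3 and r = 0.3, baseline-adjusted power at 0.78 falls to 77%.

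**7. The cited .56.** Power is 56% for the 3-month t-test. The section 7 model gives 43%, 56% and 78% (k = 1) or 53%, 66% and 84% (k = 0.7), and the baseline-adjusted analysis gives 60%, 69% and 84%. The two effects differ by 0.78/0.56 = 1.39, that is 39%.

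**The case against.** The strongest reply is that no figure in the plan is wrong. The stated inputs give 84% for a 3-month comparison against a claimed 80%. That stands, and it rules out the tempting inference that the trial is too small or the 80% miscalculated. A shortfall under the section 7 model needs near-equal SDs together with r below about 0.45, and the documents give neither. The entry threshold may lower r, but it may also narrow the baseline SD, which helps the change analysis: at SD ratio 0.7 no value of r in the assumed range falls below 80%. The power text also speaks of an effect-size improvement, which could mean SDs of change. The reference to 3-month follow-up favours 3-month units but does not settle it.

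A reader might also infer that the trial is underpowered for its expected effect, because section 2 speaks of moderate improvements and .56 is cited. The documents do not support this. Section 2 is hedged and gives no number. The .56 is disclosed, no power is claimed for it, it is not said to be on the PHQ-9, and the higher planning value is attributed to therapist support. Calling a 39% difference slight is loose wording and no more.

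Finally, the main purpose is feasibility, and the complete-data fit is only the first analysis, within an intention-to-treat plan. Both points lower the stakes. Neither supplies the missing test, SD and correlation, and neither recovers the precision lost by leaving out the baseline covariate.

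**Conclusion.** This is a free improvement and not an arithmetic error. As written, the PHQ-9 model compares mean change and has a standard error 24%, 15% and 8% larger than a baseline-adjusted analysis at r = 0.3, 0.5 and 0.7 with equal SDs, or about 8%, 3% and 0% larger at SD ratio 0.7. The 80% power statement holds for an unadjusted 3-month t-test. For the section 7 model it is neither shown nor refuted: 70–97% with equal SDs, 81–98% at SD ratio 0.7, or 84% throughout if 0.78 is in SDs of change. These ranges rest on assumed values of r and of the SD ratio, on complete data from 29.6 patients per arm, and on no loss from clustering.

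A reader should not conclude that baseline adjustment guarantees more than 80% power, since the planned clustering adjustment could take it below that level. The feasibility aim is not affected.

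**What to change.** 1. In section 7, estimate the PHQ-9 difference between arms at 3 months with baseline PHQ-9 and gender as covariates, keeping the planned clustering adjustment. If a mixed model in which the arms share one baseline mean is preferred, use an unstructured covariance over the two visits. Do not simply drop the arm main effect and keep the random intercept: that structure forces equal variances. In simulation with no effect, 30 per arm and SD ratio 0.7, its type I error was about 8–9% instead of 5%.

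2. In sections 4.2 and 7, name the test, the SD that defines 0.78 and the assumed r. For example: *Before any allowance for clustering, with 29.6 evaluable patients per arm, two-sided 0.05 and adjustment for baseline PHQ-9, power at 0.78 (3-month SD units) is about 87–98% for an assumed baseline to 3-month correlation of 0.3–0.7.*

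3. Optionally, give the corresponding 60–84% at the cited .56 as a lower scenario, and delete the word that calls 0.78 only slightly higher.

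The cost is one model statement and two power paragraphs. The sponsor must fix the PHQ-9 model before analysis and commit to an assumed correlation. No added enrolment, visits or data are needed.
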